2.4 Endpoints

The primary endpoint on this study is change in positional pain intensity as measured by NRS-11 pain scores (**Appendix C**) (PID₁₅= PI₀- PI₁₅). Change in NRS-11 pain scores will be calculated from the time of laying down on the hard surface (0 minutes) to the 15-minute time point. NRS-11 (at time 0 and time 15) will be collected at the radiation simulation and at each subsequent radiation therapy visit. The rationale for obtaining a PID at 15 minutes, is based on the reported intranasal fentanyl C_{max} of 15-30 min.

Secondary endpoints include pain severity difference as measured by the Brief Pain Inventory Short Form (BPIsf)¹⁸ (**Appendix D**). We will compare the BPIsf pain scores from the time of laying down on the hard surface (0 minutes) to 15 minutes after laying down at each fractionation visit. As a secondary endpoint we will also examine Lazanda safety, defined as the rate of drug-related adverse events experienced assessed according to the NCI's CTCAE v4.03 toxicity criteria.

Exploratory endpoints will include total recumbent time at each fractionation visit, measured in minutes.

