Objectives	
Primary Objective Our primary objective is to assess the change in patient reported positional pain intensity (PI) as measured by an 11-point numerical rating scale (NRS-11) in cancer patients with bone metastases assessed at each daily palliative radiation fraction. Our primary objective will be measured using the pain intensity difference (PID) of the NRS-11 from baseline to 15-minutes post administration ($PID_{15} = PI_0 - PI_{15}$).
 
Secondary Objectives Our secondary objectives are to: 1) Assess change, baseline to 15 minutes, in patient reported pain severity using the Brief Pain Inventory Short Form (BPI-sf).¹ 2) Evaluate adverse effects associated with Lazanda use utilizing the NCI CTCAE version 4.03 before and after palliative radiation. 3) Contribute to the body of knowledge to improve patient care measures that address discomfort associated with radiotherapy for patients with bone metastases.
 
Exploratory Objective To assess the impact on radiation treatment delivery efficiency. This will be quantified by determining the total time of radiation treatment.

Number of Subjects	6
Diagnosis and Main Inclusion Criteria	
Patients with a pathologically-confirmed solid tumor or hematologic malignancy with symptomatic bone metastases.
 
Key Inclusion Criteria:
 
 1. Patient is planned to receive hypofractionated palliative radiation ≤ 10 fractions. 2. Patient must be opioid-tolerant (≥ 60mg morphine or equivalent) and on a stable dose of oral opioids for ≥ 1 week. Stable baseline opioid dosage defined as a dosage that does not fluctuate by $> 50\%$ from the average dosage over one week prior to screening. 3. Patient must be on a stable dose of adjuvant pain therapies for one week prior to screening or after 4-5 half-lives of adjuvant

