
Statistical Methodology
	
Descriptive statistics will be used to characterize overall pain change (base to 15) and pain change (base to 15) per treatment day (1,...,n).
 
To analyze our secondary aim, change in our secondary aim, change in patient reported pain severity; we will use the BPI-sf. The BPI-sf will be used to calculate "worst pain" (calculated as the arithmetic mean of the four severity items measuring pain severity

	
in the BPI-sf). We will assess changes in BPI-sf using the same approach as our primary aim. Namely, change in BPI-sf “worst pain” score will be analyzed using a linear mixed-effects model to account for the repeated daily dosing. Modeling the difference in BPI-sf from baseline and 15 minutes at each fractionation visit; with a fixed effect for time and a subject level random intercept to account for within-patient variability. Descriptive statistics will be provided for overall pain severity change and pain severity change at each treatment day (1,...,n). As part of our secondary aim we will also provide descriptive statistics for adverse effects associated with Lazanda use utilizing the NCI CTCAE version 4.03 stratified as before and after palliative radiation.
 
Our exploratory aim will assess the impact of Lazanda on treatment delivery efficiency. This will be assessed by comparing treatment delivery efficiency in the Lazanda treated patients to the historic average. To assess this we will quantify each subjects average total time on the treatment table (averaged across each subjects fractionation visits, in minutes). This average will be compared to the clinic’s historic average of 6 minutes using a one-sample t-test of the null hypothesis that the average time on the treatment table for Lazanda study patients equals 6 minutes. As a further exploratory aim we will also consider the effects of baseline pain intensity score, 24-hour opioid use (oral morphine equivalents) and total treatment time at each fraction (minutes) on change in pain intensity (PID₁₅) by including each of them as fixed effects in the linear mixed-effects models.
 
This trial will enroll approximately 6 subjects meeting the eligibility criteria described above. Conservatively assuming a 10% drop out rate, this will leave an analytic sample size of 5.

--	---

SCHEDULE OF EVENTS

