	Screening (≤21 days from baseline)	Radiation Therapy Simulation ⁷ (≤14 days RT)	Radiation Fraction (Daily, up to 10 fractions)	Post Treatment Follow-Up (Daily, for 2 days)
Informed consent	X			
Medical and surgical history	X			
Demographics	X			
Eligibility criteria	X			
ECOG Performance status	X	X	X	
Document location of bone lesion	X			
Pregnancy test (if applicable) ¹	X			
Physical exam	X	Per routine care frequency		
Vital signs	X	Per routine care frequency	Per routine care frequency	
Weight	X	X	X	
Concomitant medications		X	X	X
Adverse events		X	X	X ⁴
Comprehensive metabolic panel	X ⁵	Per routine care frequency		
Record baseline 24-hour opioid dose	X			
Record total time in radiation therapy unit		X	X	
Record recumbent time		X	X	
Lazanda dispensing & administration		X ⁶	X ⁶	
Radiation Therapy (hypofractionation)			X	
Study drug diary		X	X	
Brief Pain Inventory Short Form	X	X	X	X
Numerical Rating System Pain Score ²		X	X	X
Patient medication use diary ³	X	X	X	X
Patient nausea/vomiting diary		X	X	X
Patient laxation diary		X	X	X

- 1) Females of childbearing potential only; must be performed within 72 hours of baseline.
- 2) NRS Pain Score will be collected at a total 2 events: (1) radiation therapy simulation, and (2) at each radiation fraction (up to 10 fractions total). At each event, NRS pain scores will be recorded at T-15 (15 minutes prior to laying down on treatment surface), T0 minutes (laying down on treatment surface), and T+15 after laying down on the treatment surface. (Appendix I- NRS Scale log)
- 3) To include a record of any anticancer therapy, vitamins, homeopathic/herbal remedies, nutritional supplements, opioid medication use, over-the-counter analgesics, and all other over-the-counter and PO medication use.
- 4) Patients will be monitored for adverse events until 30 days following the last study drug administration.
- 5) Serum chemistries performed within six weeks of baseline may be used to fulfill screening requirements.
- 6) Lazanda will be self-administered by the subject 15 minutes (± 5 minutes) prior to laying on the hard surface.
- 7) If the 100-mcg dose does not achieve adequate pain control at the first assessment of the simulation visit, the subject will receive a second dose 2 hours later as per label until the optimal dose is obtained. If not practical the subject will delay or reschedule the next assessment of the simulation (within a 14 days period) or XRT delivery.

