2.0 STUDY OBJECTIVES

2.1 Primary Objectives

Our primary objective is to assess the change in patient reported positional pain intensity (PI) as measured by an 11-point numerical rating scale (NRS-11) in cancer patients with bone metastases assessed at each daily palliative radiation fraction. Our primary objective will be measured using the pain intensity difference (PID) of the NRS-11 between 0 minutes and 15 minutes after laying down on the hard surface ($PID_{15} = PI_0 - PI_{15}$).

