4.0 TREATMENT PLAN

4.1 Study Design

This is a phase II, single-center, open-label study. We anticipate recruitment of approximately 15 total study participants at the UCSD Moores Cancer Center. Study participants will be recruited across all oncology disease teams. Potential participants will be identified in weekly palliative care or disease team patient triage meetings.

To meet eligibility for participation, a patient must be greater than or equal to 18 years old, have histologically-confirmed cancer with symptomatic bone metastases, an ECOG performance

status less than or equal to 3, and are planned to receive hypofractionated palliative radiation less than or equal to 10 fractions. Qualifying subjects must be opioid-tolerant, defined as greater than or equal to 60mg morphine or equivalent, and be on a stable dose of oral opioids for greater than or equal to 1 week. Stable baseline opioid dosage is defined as a dosage that does not fluctuate by more than 50% from the average dosage over one week prior to screening. Patients must also be on a stable dose of adjuvant pain therapies for one week prior to screening or after 4-5 half-lives of adjuvant pain therapies. Patients will be excluded if they are receiving or have received another investigational agent within 30 days or monoamine oxidase inhibitor within 14 days prior to Lazanda administration, have known hypersensitivity to fentanyl or opioids, have known, planned interventional procedures such as surgery that may affect study outcomes, are pregnant or nursing, have a disorder or current medication use likely to adversely affect normal functioning of the nasal mucosa, have uncontrolled or rapidly escalating background pain, or are medically unstable.

The primary objective of this study is to assess the change in patient reported positional pain intensity (PI) as measured by an 11-point numerical rating scale (NRS-11) (**Appendix C**) in cancer patients with bone metastases assessed at a simulation visit and each subsequent daily palliative radiation fraction. Our primary objective will be measured using the pain intensity difference (PID) of the NRS-11 from the time of laying down on the hard surface (0 minutes) to the 15 minutes after laying down on the hard surface timepoint at baseline (the simulation visit) and at each subsequent study visit ($PID_{15} = PI_0 - PI_{15}$).

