Lazanda titration should be done with caution in patients with chronic obstructive pulmonary disease or preexisting medical conditions predisposing them to respiratory depression and in patients susceptible to intracranial effects of CO₂ retention. Caution should also be used in patients on central nervous system (CNS) depressants and potent CYP3A4 inhibitors.

The minimal effective intranasal dose from the radiation therapy simulation will be the dose used as pre-medication prior to any further radiation therapy fractions (up to 10 fractions). Lazanda should be administered 15 (T-15) minutes prior to laying on the hard surface for each simulation visit. If the response to the titrated Lazanda dose markedly changes, an adjustment of dose may be necessary to ensure that an appropriate dose is maintained as deemed by the investigator.

Subjects will be instructed on the proper use of Lazanda as follows:

- 1) Prime the device before use by spraying into the pouch (4 sprays in total). If study drug has not been used for 5 days, re-prime by spraying once.
- 2) Insert the nozzle of the Lazanda bottle a short distance (about ½ inch) into the nose and point towards the bridge of the nose, tilting the bottle slightly.
- 3) Press down firmly on the finger grips until hearing a “click” and the number in the counting window advances by one.

Subjects will also be advised that the fine mist spray is not always felt on the nasal mucous membrane and to rely on the audible click and advancement of the dose counter to confirm a spray have been administered.

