9.3.1 Primary Analysis

Our primary aim of assessing the change in NRS-11 scores of patients before and after receiving Lazanda will be analyzed using a linear mixed-effects model to account for the repeated daily dosing. We will model the difference in PID from baseline to 15 minutes (PID₁₅) at each radiation simulation and fractionation visit; with a fixed intercept term for time and a subject level random intercept to account for within-patient variability. We will provide descriptive statistics overall and for each treatment day (day 1, ..., n). Descriptive statistics will include mean/standard deviation, min, max and IQR.

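### PID15 compares two scores that are both nominally taken after the spray, so it cannot answer the before-and-after aim in 9.3.1 and does not match the interval in the Study Summary

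*Combined protocol and SAP*

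**What the plan says.** **Definition of PID15.** Section 2.1 takes the difference "between 0 minutes and 15 minutes after laying down on the hard surface". Section 2.4 agrees: "Change in NRS-11 pain scores will be calculated from the time of laying down on the hard surface (0 minutes", up to the 15-minute point. Section 4.1 has it run "from the time of laying down on the hard surface (0 minutes) to the 15 minutes after laying down on the hard surface timepoint", and 6.2 and 9.1 use the same interval.

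**Time of the spray.** Footnote 6 of the Schedule of Events covers both simulation and fractions: "Lazanda will be self-administered by the subject 15 minutes", with a tolerance of 5 minutes either way, before lying on the hard surface. Section 4.2.1 repeats the nominal time for simulation: "Lazanda should be administered 15 (T-15) minutes prior to laying on the hard surface for each simulation visit".

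**Stated aim.** Section 9.3.1 gives the primary aim as "assessing the change in NRS-11 scores of patients before and after receiving Lazanda" and models PID15 as a change from baseline to 15 minutes.

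**Study Summary.** The objective prints PI0 − PI15 but describes it as the "pain intensity difference (PID) of the NRS-11 from baseline to 15-minutes post administration". The statistical paragraph says "Descriptive statistics will be used to characterize overall pain change (base to 15", without saying what base is.

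**T-15.** A score 15 minutes before lying down is collected at simulation and at every fraction (Schedule of Events, 4.1, 5.1.11.1, 5.3.1, 5.3.2, Appendix I). No analysis uses it, and no section says whether it is taken before or after the spray.

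**The concern.** The rationale in 1.3 is to treat table pain in advance with a rapid-onset opioid. If that works, part of the relief may already be present when the patient lies down. That relief lowers PI0, so PID15 does not count it. Followed as written, the primary result is a change between two on-drug scores, reported against an aim that calls for a pre-drug score.

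Two analysts could also compute different primary results: one from the interval in 2.4, the other from the interval in the Study Summary. And if the T-15 score is taken after the spray at some visits, those visits have no pre-drug score and none can be reconstructed.

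**Working it through.** The plan gives no figure for this point. The SD of 1.48 in 9.2 does reproduce from the assumed IQR of 2 (2/1.349 = 1.48), but that section does not say which interval it refers to. The check is therefore clock arithmetic.

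**1. Minutes after the dose** (spray 15 ± 5 min before T0, Schedule of Events footnote 6)
- PI0, at T0: 15 ± 5 = 10 to 20 min.
- PI15, at T+15: 15 + 15 ± 5 = 25 to 35 min.

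Both scores are nominally on drug. Section 2.4 justifies the 15 minutes by a 15-30 minute peak, but that clock runs from administration, and T0 nominally already falls in that range.

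One exception is possible. Section 4.2.2 lets a forgotten dose be taken later the same day before radiation, whereas Appendix H tells the patient to skip it. Those two instructions conflict and must be reconciled.

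**2. The Study Summary interval against PID15** (the former ends 15 min after the spray)
- Spray at T-15: ends at T0, overlap 0 min.
- Spray at T-10: ends at T+5, overlap 5 of 15 min.
- Spray at T-20: ends at T-5, gap of 5 min.

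**3. T-15 against the spray.** The spray may fall anywhere from T-20 to T-10. A score taken exactly at T-15 is therefore anywhere from 5 min after to 5 min before it.

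**4. What PID15 cannot distinguish** (invented scores, not an estimate)

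| T-15 / T0 / T+15 | T0 − T+15 | T-15 − T0 |
|---|---|---|
| 6 / 1 / 1 | 0 | 5 |
| 6 / 6 / 6 | 0 | 0 |

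The scale also sets a limit. NRS scores run from 0 to 10 (5.1.11.1), so PID15 ≤ PI0. A visit with PI0 of 0 or 1 cannot show a 2-point fall, the decrease that 1.2 reports from earlier work. Any difference score is bounded by its own starting score; it matters here because the starting score is taken on drug.

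**5. Which baseline?** Section 4.1 calls the simulation visit baseline, and that visit is dosed. The same section calls the screening NRS baseline, and 5.2 collects it. Footnote 2 of the Schedule of Events and 5.1.11.1 list only simulation and fractions as NRS events. Section 9.3.1 and the baseline pain covariate in 2.3 and 9.3.4 do not say which score is meant.

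**6. Number of scores per visit.** Sections 5.3.1 and 5.3.2 list five (T-15, 0, 5, 10 and 15 min). The Schedule of Events, 4.1, 5.1.11.1 and Appendix I list three. This is a separate inconsistency in the same data.

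**The case against.** The best defence is that the primary objective is positional pain. Read alone, 2.1 matches T0 to T+15 exactly, and the choice of contrast belongs to the sponsor. The study is a case series of about 6 patients with no decision rule on PID15. T-15 scores and exact rating and spray times are already recorded (4.1, 4.2.2), so further contrasts can be specified before analysis. All of that stands, and it limits how serious the point is. It does not remove the conflict with 9.3.1 and the Study Summary.

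A reader might infer that the drug-effect statements in 6.2 and 9.3.4 rest on PID15 alone. They do not. Section 6.2 draws on NRS and BPI-sf through follow-up, and 9.3.4 on NRS, BPI-sf and adverse events together. The documents support only the narrower statement that PID15 by itself cannot carry that reading.

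A reader might also infer that the trial holds no pre-drug pain score. The screening NRS in 4.1 and 5.2 precedes any study drug, although it enters no PID15 definition. The Mock/Baseline Visit row in Appendix I is separate from the Lazanda rows and may be an undosed lying-down assessment, but the body does not describe it.

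Finally, contrasts from T-15 have their own weakness. They mix drug effect with pain provoked by lying down, and they can be negative with a working drug. At later same-day titration steps T-15 is not drug-free: 4.2.1 allows a further dose after 2 hours, and 1.2 gives a half-life of 5.5 to 9.7 hours. This stands, so they can only be descriptive.

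**Conclusion.** The point holds as an inconsistency between the endpoint and its stated aim, and it should be fixed. With the spray 15 ± 5 minutes before lying down, PID15 nominally spans 15 to 30 minutes after the dose. It overlaps the Study Summary interval by 0 minutes nominally and by at most 5 of 15 within the window. It is valid as an on-drug positional change and cannot serve as a before-and-after-drug comparison.

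The relief missed by PID15 cannot be sized from the documents. It is tempting to divide the 2-point response rates in 1.2, 49% at 15 minutes by 63% at 30 minutes (49/63 = 78%), and call that the share of effect lost before T0. The documents do not support this. These are response rates in breakthrough pain, quoted without placebo rates; they are not shares of an effect on positional pain. The report that pain scores differed from placebo at 10 and 15 minutes shows only that some effect may precede PI0.

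Nor should a reader conclude that moving the baseline to T-15 would isolate the drug effect. No contrast in this uncontrolled study does that.

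The conclusion assumes dosing within the footnote 6 window, with late doses as exceptions. The one time-critical part is the order of the T-15 score and the spray; the rest can be settled before analysis.

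**What to change.** 1. State in the Schedule of Events, 4.1 (text and Summary of Assessments table), 5.1.11.1, 5.3.1, 5.3.2 and Appendix I that the T-15 NRS is recorded immediately before the spray.
2. Use one PID15 interval and one named baseline in the Study Summary (objective and statistical paragraph), 2.1, 2.4, 4.1, 6.2, 9.1 and 9.3.1. If T0 to T+15 stays primary, label it an on-drug positional change. In that case also remove the post-administration wording from the Study Summary objective and the before/after wording from 9.3.1.
3. Pre-specify T-15 to T0 and T-15 to T+15 per visit as descriptive pre-dose to post-dose changes, using the actual rating and spray times. State the limits given above: positional pain is mixed in, T-15 is not drug-free at later same-day titration steps, and neither these changes nor PID15 isolates a drug effect.
4. Say whether the Mock/Baseline Visit row in Appendix I is an undosed lying-down assessment. If it is, describe it in the body and report it as the positional reference.
5. Name the score that serves as the baseline pain covariate in 2.3 and 9.3.4: the screening NRS, T-15 or T0.
6. Separately, reconcile the five NRS times with the three, and reconcile 4.2.2 with Appendix H on a forgotten dose.

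Items 1 to 5 cost wording changes and two extra summaries from scores and times already recorded. They add no visit or score and change no dose. The price is interpretive: the report must say plainly what each contrast cannot show.

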Secondary objectives will seek to assess patient reported pain severity using the BPI-sf (**Appendix D**), and evaluate adverse effects associated with Lazanda use utilizing the NCI CTCAE version 4.03 before and after palliative radiation.

Exploratory objectives will assess the impact on radiation treatment delivery efficiency, which will be quantified by determining the total time of radiation treatment, defined as the average time on the treatment table for each fractionation visit. A second exploratory objective will be to examine the effect of: baseline pain intensity score, 24-hour opioid use (oral morphine equivalents) and total treatment time at each fraction (minutes) on change in pain intensity (PID15)

After obtaining written informed consent, patients will have the following procedures completed to confirm eligibility: physical exam with vital signs and weight, ECOG performance status, comprehensive metabolic panel, and a serum pregnancy test (women of child-bearing potential only). During this screening period, patients will also complete a baseline NRS pain score and BPI-sf questionnaire (**Appendix D**), and report baseline 24-hour opioid dose.

Event	NRS-11	BPI-sf	Diaries		
			Medication Use	Nausea Vomiting	Laxation
Simulation	T-15, T0, T+15	T15+	X	X	X
Daily radiation fraction	T-15, T0, T+15	T15+	X	X	X

Table 1: Summary of Assessments; NRS-11 = numerical rating scale; BPI-sf = Brief Pain Inventory short form; T-15= 15 minutes prior; T0=at point of laying down; T+15 = 15 minutes after layind down; T15+ = any point after 15 minutes from laying down; X = once daily

Simulation Evaluation

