The subject will then undergo radiation therapy simulation procedures (within approximately 2 weeks of radiation therapy) followed by hypofractionated radiation therapy, according to UCSD Radiation Oncology standard procedure and treatment plan determined by the subject’s radiation oncologist. During radiation simulation and daily during each visit to the radiation center for hypofractionation delivery, subjects will have vital signs and weight collected per routine care. An ECOG performance status will also be assessed daily during radiation therapy. At the time of radiation simulation and daily during radiation therapy, subjects will complete the BPI-sf (**Appendix D**), Medication Use Diary (**Appendix E**), Laxation Diary (**Appendix F**), and Nausea/Vomiting Diary (**Appendix G**). NRS pain scores will also be collected at three time points during each visit to the radiation center: 15 minutes prior to laying on the hard surface (T-15), at the time of laying on the hard surface (T0), and at 15 minutes after laying on the hard surface(T+15). Exact time of each pain score rating will also be collected. The study coordinator will record total time in radiation therapy unit and total recumbent time (time laying down) during the simulation and each radiation treatment visit. Additionally, radiation treatment parameters, the presence of any adverse effects (NCI CTCAE v 4.03), and concomitant medications will be recorded.

Lazanda Dosing During Simulation

Subjects will receive study drug, Lazanda at 100mcg dose, 15 minutes prior to simulation (T-15) at the radiation therapy simulation visit. Lazanda dose titration will follow the guidelines as indicated in the product package insert from the radiation simulation visit through the end of radiation therapy. Lazanda dose titration procedures are further detailed in **Section 4.2**.

Subjects will undergo a post treatment follow-up period after completion of their radiation therapy. During this follow-up period, subjects will complete the BPI-sf (**Appendix D**), Medication Use Diary (**Appendix E**), Laxation Diary (**Appendix F**), and Nausea/Vomiting Diary (**Appendix G**) daily for 2 days. Concomitant medication use will also be recorded. Subjects will be monitored for the presence of any adverse effects (NCI CTCAE v 4.03) until 28 days following their last dose of Lazanda.

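### The secondary BPI-sf endpoint in section 2.4 is a 0-to-15-minute change at each fraction, but no time-0 BPI-sf is scheduled, so it cannot be computed at any visit

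*Combined protocol and SAP*

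**What the plan says.** **The endpoint.** Section 2.4 sets the BPI-sf comparison within each fractionation visit: "We will compare the BPIsf pain scores from the time of laying down on the hard surface (0 minutes) to 15 minutes" later. The Study Summary gives the objective as "Assess change, baseline to 15 minutes, in patient reported pain severity using the Brief Pain Inventory Short Form (BPI-sf"), and its statistical paragraph adds "We will assess changes in BPI-sf using the same approach as our primary aim". Section 9.3.3 models a baseline-to-15-minute difference in the BPI-sf score at simulation as well as at each fraction.

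**The schedule.** Table 1 in section 4.1 gives the NRS-11 three times per visit (T-15, T0, T+15). It gives the BPI-sf one entry, which the table note explains as "T15+ = any point after 15 minutes from laying down". The text of 4.1 says only "At the time of radiation simulation and daily during radiation therapy, subjects will complete the BPI-sf", alongside the diaries, and keeps the three time points for the NRS. There is also a screening form: "patients will also complete a baseline NRS pain score and BPI-sf questionnaire". Two further forms fall on the post-treatment follow-up days.

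**The score.** The Study Summary and 9.3.3 both define it as the average of the four severity items, and both call it *worst pain*.

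**The concern.** A difference between two time points needs a measurement at each. The BPI-sf is the only secondary efficacy endpoint in 2.4, and its starting value is never collected. An analyst who follows the plan would have nothing to put in the 9.3.3 model. The likely outcome is a substitute reference chosen once the data are in hand, in a study of about six subjects where that choice could shape the reported result. The timing also invites readers to see the BPI-sf result as an acute response to Lazanda, which a form with 24-hour recall is not built to show.

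**Working it through.** The plan gives no sample size, power or expected change for the BPI-sf, so there is no figure to reproduce. The check is a count of scheduled forms, followed by a look at what the form can measure.

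**1. Every place that schedules the BPI-sf at a dosing visit**

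| Place | BPI-sf | Time-0 form? |
|---|---|---|
| Schedule of Events | one untimed X per column; footnote 2 gives clock times for the NRS only | no |
| 4.1, Table 1 | T15+ at simulation and each fraction | no |
| 4.1, text | at simulation and daily; three time points for the NRS only | no |
| 5.3.1 (simulation) | one untimed entry | no |
| 5.3.2 (fractions) | one untimed entry in a daily list | no |

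**2. Count**
- Visits under 9.3.3: 1 simulation + up to 10 fractions = 11. This assumes one simulation visit.
- Forms at T15+: 11. Forms at time 0: 0. Computable within-visit differences: 0 of 11.
- Counting fractions only, as 2.4 does: 0 of 10.
- Repeating the simulation raises the denominator and leaves the numerator at 0.

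The later time is not fixed at 15 minutes either, because T15+ has no upper limit.

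**3. What baseline means in 9.3.3**

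For the NRS-11, the Study Summary and 9.3.1 use the same baseline-to-15-minute wording for PID15, which is PI0 minus PI15. Read the same way, 9.3.3 also means time 0 and meets the same gap. The Study Summary counts the NRS-11's 15 minutes from administration. On that clock too, no earlier BPI-sf exists within the visit.

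**4. Would a time-0 form help?**

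Section 5.1.11.2 puts completion at about 5 minutes and says the form is validated for 24-hour recall. Section 5.1.11 asks for a quiet area. In Appendix D, items 3 and 4 cover the last 24 hours, item 5 asks for average pain, and only item 6 asks about pain at that moment. If item 6 alone falls by d points, the four-item mean falls by d/4:
- d = 1: 0.25
- d = 2: 0.50
- d = 3: 0.75

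So three quarters of an acute change would be averaged away.

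**5. Which forms precede Lazanda?**

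Footnote 6 of the Schedule of Events allows dosing 15 ± 5 minutes before lying down. The simulation form therefore comes at least 10 + 15 = 25 minutes after the first dose. Only the screening form is completed before any Lazanda.

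**6. Age of the screening form**

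Assume that baseline in the Schedule of Events means simulation. Then the form may be up to 21 + 14 = 35 days old at fraction 1. The Study Summary's 4 to 5 weeks of participation (28 to 35 days) would keep it younger. Section 5.2 counts the 21 days to registration instead, which could make it older.

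**The case against.** The strongest reply is that BPI-sf reporting is not empty. Section 2.2 states the objective as a change in pain severity with no 15-minute limit. Section 6.2 follows the BPI-sf from baseline through follow-up. Section 9.3.3 also promises summaries by treatment day, which the T15+ forms can supply. This stands, and it limits the point to the within-visit change.

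One can also say that the Study Summary's reference to the primary approach may mean only the mixed model. That is fair, but the same paragraph then describes a baseline and 15-minute difference at each fractionation visit, so the gap remains.

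Two stronger readings are tempting and not supported:

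- *A reader might infer that baseline for the BPI-sf is simply undefined, with screening and simulation as rival definitions.* The phrase "at baseline (the simulation visit) and at each subsequent study visit" is written about the NRS-11 difference. In the screening sentence of 4.1, the word baseline sits directly before the NRS score, and its reach to the BPI-sf is arguable. No section says that the BPI-sf change runs from screening or from simulation. The natural reading is time 0.
- *A reader might infer that the analysed score is ambiguous because it is called worst pain.* Both places state the formula, so the computation is clear. This is a naming slip: in Appendix D, worst pain is item 3 alone.

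Finally, the choice of replacement belongs to the investigators. The defect obliges them to reconcile the sections and does not dictate one estimand.

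**Conclusion.** The point holds for the within-visit endpoint. As defined in 2.4 and repeated in the Study Summary and 9.3.3, the BPI-sf change can be computed at 0 of up to 11 visits, however many subjects enrol. This rests on Table 1 being the full timing specification, and no other section adds a form. By-day descriptive summaries of the T15+ score remain possible.

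The consequence is moderate. A reader might infer that the trial's main result is compromised. It is not: the NRS-11 has its own T0 and T+15 scores, and no decision rule uses the BPI-sf. It should be fixed before any analysis because the repair is cheap now and would look data-driven later.

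**What to change.** **Needed in any case.** Reconcile the Study Summary (objective and statistical paragraph), 2.4 and 9.3.3 with Table 1 by deleting the 0-to-15-minute, or baseline-to-15-minute, change for the BPI-sf. Name the same visits in all three places; at present 9.3.3 includes simulation, while 2.4 and the Study Summary's statistical paragraph name fractions only. Call the four-item mean *pain severity*.

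**Replacement from forms already scheduled.** Suggested text: *The BPI-sf endpoint is the change in pain severity (mean of items 3 to 6) from the screening form to the form completed at each named visit. It is a descriptive day-to-day change and is not interpreted as an acute effect of Lazanda.* This agrees with 2.2 and 6.2 and uses the only form completed before any Lazanda.

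**Cost.** No new forms or visits, but this is a different estimand and needs an amendment approved by the IRB under 10.10. The reference form may be several weeks old. The change will also reflect radiation, the opioid adjustments that 4.4 permits, and elapsed time. All of a subject's changes share one screening value.

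**Alternative.** If the investigators want to keep the 0-to-15-minute timing, collect item 6 alone at T0 and T+15. That means up to 2 × 11 = 22 single-item ratings per subject and a change to Table 1, and it largely duplicates the NRS-11.
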